7 ADVERSE EVENT AND TOXICITY MANAGEMENT

7.1 Adverse Events

7.1.1 Definition of AE

An adverse event (AE) will be defined as any new unfavorable or unintended sign, symptom, or disease, or change of an existing condition, which occurs during or after treatment, whether or not considered treatment-related. If clinically significant laboratory value lead to or are associated with clinical symptom(s), the diagnosis should be reported as an AE. The lack of drug effect is not any AE in clinical trials because the purpose of the clinical trial is to establish drug effect.

An AE does not include the following:

- Medical or surgical procedure such as surgery, endoscopy, tooth extraction, and transfusion. The condition that led to the procedure may be an AE and must be reported.
- Pre-existing disease, condition, or laboratory abnormalities present or detected before the screening visit that do not worsen.
- Situations where an untoward medical occurrence has not occurred (e.g. hospitalization for elective surgery, social, and/or convenience admissions).
- Overdose without clinical sequelae.
- Any medical condition or clinically significant laboratory abnormality with an onset date before the consent form is signed and not related to a protocol-associated procedure is not

an AE. Such condition or abnormality is considered a pre-existing and should be documented on the medical history in the CRF.

Prior to enrollment, study personnel will note the occurrence and nature of each subject's medical condition(s) in the Medical History section of the CRF. During the remainder of the study, study personnel will again note any change in the condition(s) and the occurrence and nature of any adverse events.

If a subject experiences an AE after the Informed Consent document is signed (entry) but the subject is never assigned to treatment (enrollment), the event will only be reported if the investigator believes that the event may have been caused by a protocol procedure.

Adverse event information will be collected from the time subject signs the informed consent and until the end of the subject's study participation, i.e. Study Week 48 (end-of-study visit) or earlier if consent has been withdrawn. All AEs occurring after the subject has entered the study (that is, after the Informed Consent document is signed) must be recorded in the CRF. If the study drug is discontinued for a subject, study personnel must report and clearly document the circumstances and data leading to any such discontinuation, using designated CRFs. For AEs, the subject should be followed until the event resolves or stabilizes, with frequency of follow-up at the discretion of the investigator.

In case the investigator notices an unanticipated benefit to the subject, study personnel should enter "unexpected benefit" with the actual event term (for example, the complete actual term would be "unexpected benefit – sleeping longer").

Cases of pregnancy that occur during maternal or paternal exposures to study drug should be reported for tracking purposes. Data on fetal outcome and breastfeeding are collected for regulatory reporting and drug safety evaluation.

7.1.2 Reporting Procedures for All Adverse Events

The investigators are responsible for monitoring the safety of subjects who have entered this study and noting any event that seems unusual, even if this event may be considered an unanticipated benefit to the subject. The investigator is responsible for appropriate medical care of subjects during the study.

The investigator remains responsible for following, through an appropriate health care option, AEs that are serious or that causes the subject to discontinue the study. The subject should be followed until the event is resolved or explained. Frequency of follow-up will be left to discretion of the investigator.

7.1.3 Adverse Events Severity

The **Division of AIDS (DAIDS) Table for “Grading the Severity of Adult and Pediatric Adverse Events” corrected version 2.1 (July 2017)** will be used to assess and grade AE severity, including laboratory abnormalities judged to be clinically significant. If the experience is not covered in the DAIDS criteria, the following guidelines should be used to grade severity:

- **Mild (grade 1):** Mild symptoms causing no or minimal interference with usual social and functional activities with intervention not indicated.
- **Moderate (grade 2):** Moderate symptoms causing greater than minimal interference with usual social and functional activities with intervention indicate.
- **Severe (grade 3):** Severe symptoms causing inability to perform usual social and functional activities with intervention or hospitalization indicated.
- **Life-threatening (grade 4):** Potentially life-threatening symptoms causing inability to perform basic self-care functions with intervention indicated to prevent permanent impairment, persistent disability, or death.

The term “severe” is a measure of intensity and a severe AE is not necessarily serious.

7.1.4 Adverse Event Relationship to Study Drug

The investigator or qualified subinvestigator is responsible for assessing the relationship to study drug therapy using clinical judgment and the following considerations:

- **Yes (reasonably related):** There is reasonable possibility that the event may have been caused by the study drug.
- **No (not related):** Evidence exist that the adverse event has an etiology other than the study drug. For SAEs, an alternative causality must be provider (e.g., pre-existing condition, underlying disease, intercurrent illness, or concomitant medication).

Ineffective treatment should not be considered as causally related in the context of adverse event reporting.

7.1.5 Adverse Event Expectedness

The investigator will be responsible for determining whether an adverse event is expected or unexpected. An AE will be considered unexpected if the nature, severity, or frequency of the event is not consistent with the risk information previously described for the study intervention.

7.2 Serious Adverse Events

7.2.1 Definition of SAE

A serious adverse event (SAE) is defined as an AE that suggests a significant hazard or side effects, regardless of the relationship to study drug. An SAE includes, but may not be limited to, any event that:

- Results in Death.
- Is life threatening. This definition implies that the subject, in the view of the investigator, is at immediate risk of death from the event. It does not include an event that, had it occurred in a more serious form, might have caused death.
- Requires inpatient hospitalization or prolongation of existing hospitalization.
- Results in persistent or significant disability/incapacity.
- Results in congenital anomaly or birth defect.

Medical and scientific judgment will be exercised in deciding whether classification of an AE as serious is appropriate in other situations, such as important medical events that may not be immediately life threatening or result in death or hospitalization, but may jeopardize the subject or require intervention to prevent one of the outcomes listed in the definition above. Examples of medically important events include intensive treatment in an emergency room or at home for allergic bronchospasms; development of drug dependency or drug abuse. Infections resulting from contaminated medicinal product will be considered a medically important event.

7.2.2 Reporting of SAE

All SAE will be reported to the IRB per institutional guidelines. SAEs (regardless of relationship) must be reported to Gilead Pharmacovigilance and Epidemiology (PVE) Office **within fifteen (15) calendar days** of first becoming aware of the event. In turn, the study sponsor will be responsible for reporting any unexpected fatal or life-threatening suspected adverse reactions to the Division of Antiviral Agents at the FDA no later than seven (7) calendar days after receipt of the information. Safety reporting to the FDA will be done within the reporting requirement under 21 CFR 312.32.

The Gilead PVE Office will be notified via fax or email of any potential safety issues or any protocol amendments or changes to the informed consent arising from a safety concern associated with any Gilead products **within fifteen (15) days** of first becoming aware of such event. Except for periodic safety reports, copies of all reports submitted to government agencies that are related to the study, as well as any correspondence with any such authorities will be provided to Gilead Sciences.

Contact information:

Gilead Sciences Inc., Pharmacovigilance and Epidemiology (PVE)

[name]

[contact]

[contact]

Email: [contact]

7.3 Laboratory Tests

Clinical laboratory tests will be performed at the time specified in the Study Schedule (see Section 12: Schedule of Activities). All clinical laboratory assessments will be analyzed through a designated laboratory.

The investigator must further evaluate laboratory values that fall outside a clinically accepted reference range or values that differ significantly from previous values. Investigators must also document their review of each laboratory report by signing or initialing and dating each report.

Clinically significant laboratory abnormalities will be reported as AEs.

7.4 Reporting of Events to Participants

Any adverse event or serious adverse event that affects the risk/benefit ratio to subjects will prompt a revision to the informed consent document. All subjects will be notified of the additional risk and re-consented at their next visit, or earlier if the situation requires.

7.5 Reporting of Pregnancy

Pregnancy itself is not an adverse event. However, complications of pregnancies are AEs and may be SAEs. Pertinent obstetrical information of all pregnancies will be reported to the Gilead PVE via fax or email **within fifteen (15) calendar days** from site awareness of the pregnancy. . The participant will be advised to notify her obstetrician of study agent exposure.

Pregnancy outcome data (e.g., delivery outcome, spontaneous, or elective termination of the pregnancy, presence or absence of birth defects, congenital abnormalities, or other complications) will be reported to the Gilead PVE Office **within fifteen (15) calendar days** of the site awareness on a protocol-specified form.

7.6 Toxicity Management

All clinical and clinically significant laboratory toxicities will be managed according to uniform guidelines detailed in [Appendix C](#) as outlined below.

- Clinical events and clinically significant laboratory abnormalities will be graded according to the **Division of AIDS (DAIDS) Table for “Grading the Severity of Adult and Pediatric Adverse Events” corrected version 2.1 (July 2017)**.
- Grade 3 and 4 laboratory abnormalities that are found to be clinically significant should be confirmed by a repeat testing **within 3 calendar days** of awareness of the results and before study drug discontinuation, unless such a delay is not consistent with good medical practice.

7.6.1 Grade 1 and 2 Laboratory Abnormality or Clinical Event

- Continue study drug at the discretion of the Investigator.

7.6.2 Grade 3 Laboratory Abnormality or Clinical Event

- For Grade 3 clinical AE or clinically significant laboratory abnormality that is considered unrelated to the study drug, the study drug may be continued.
- For Grade 3 clinical AE or clinically significant laboratory abnormality that is considered to be related to study drug confirmed by repeat test, the study drug should be withheld until the toxicity returns to \leq Grade 2.
- When restarting study drug following resolution of the adverse event, the study drug should be restarted at full dose.
- If a laboratory abnormality recurs to \geq Grade 3 following rechallenge with study drug and is considered related to the study drug, then the study drug should be permanently discontinued and the subject managed according to local standard of care practice. Recurrence of laboratory abnormalities considered unrelated to study drug may not require permanent discontinuation and study drug may be continued according to the discretion of the Investigator.

7.6.3 Grade 4 Laboratory Abnormality or Clinical Event

- For Grade 4 clinical AE or clinically significant laboratory abnormality confirmed by repeat testing that is considered related to the study drug, the study drug should be permanently discontinued and subject managed according to local standard of care practice. The subject should be followed as clinically indicated until the laboratory abnormality returns to baseline or is otherwise explained, whichever occurs first. Clinically significant Grade 4 laboratory abnormality that is not confirmed by repeat testing should be management according to the algorithm for the new toxicity grade.

- Study drug may be continued without dose interruption for a clinically non-significant Grade 4 laboratory abnormality (e.g., Grade 4 triglyceride elevation that is nonfasting or that can be medically managed) or a clinical event considered unrelated to study drug.

7.6.4 On-Treatment ALT Flare and Exacerbation of Hepatitis B Management

On-treatment ALT flare is defined as:

- Confirmed (within 3 days of awareness of initial laboratory results) serum ALT > 2 x Day 1 value and >10 x ULN, with or without associated symptoms.

7.6.4.1 Management of ALT Flare in Subjects Receiving Study Medications

If laboratory results indicate elevation of ALT > 2 x Day 1 value and > 10 x ULN, the following is recommended:

- Schedule the subject to return to the clinic as soon as possible (ideally within 3 days after initial laboratory results were drawn). During the visit, a clinical assessment of the subject will be performed. The assessment should include a physical examination and evaluation of the subject's mental status.
- If the ALT elevation is confirmed, check labs for plasma HBV DNA reflex to genotype and drug resistance testing, HBV serology, HDV, HAV IgM, and HCV.

Recommend to check the following laboratory parameters: serum ALT and AST, total bilirubin, INR, and serum albumin. Based on the results of the confirmatory tests, the following treatment modifications are recommended:

If Normal or Stable Total Bilirubin or INR related to Day 1 Liver Function Test

If ALT levels are elevated (i.e., >2 x Day 1 and >10 x ULN) with normal or stable total bilirubin and INR related to Day 1, the subject may remain on study medication and should be monitored weekly until ALT levels return to normal or Day 1 level. During monitoring, if the ALT values remain persistently elevated, the Investigator has the discretion based on clinical judgment whether to withhold study drug or not.

If Elevated Total Bilirubin or INR related to Day 1 Liver Function Test

If ALT levels are elevated (i.e., >2 x Day 1 and >10 x ULN), with total bilirubin confirmed to be 2 x Day 1 value, and INR level is 0.5 above Day 1, provided both are >ULN, the Investigator should consider discontinuing study medication (unless the safety of the patient is of immediate concern). The subject should be monitored weekly as long as ALT, total bilirubin, and INR values remain elevated or above Day 1 values.

During monitoring, if the ALT values and the liver function tests remain persistently elevated, and no alternative cause other than the study drug has been found, the Investigator should discuss with a member of the Safety Monitoring Committee whether the study drug should be discontinued.

7.6.4.2 Management of Exacerbation of Hepatitis B in Subjects who have Discontinued Study Medication

If laboratory results indicate (1) an ALT elevation $>2 \times$ Day 1 and $>10 \times$ ULN alone OR associated with (2) abnormal laboratory parameters suggestive of worsening hepatic function (total bilirubin $>2 \times$ Day 1, INR >0.5 above Day 1, provided both are $>$ ULN) and the subject is on no post-study therapy for HBV, the following is recommended:

- Schedule the subject to return to the clinic as soon as possible (ideally no later than 3 days after the initial laboratory values were drawn). During the visit, perform a clinical assessment of the subject.
- Check the following laboratory parameters: serum ALT and AST, bilirubin, INR, and albumin.
- If the ALT elevation is confirmed, check labs for plasma HBV DNA reflex to genotype and drug resistance testing, HBV serology (HBsAg and HBsAb), HDV, HAV IgM, and HCV. If serum HBV DNA is increasing, the Investigator should consider immediate initiation of approved HBV therapy.
- The subject should be followed until laboratory parameters (ALT, total bilirubin, INR) return to normal or Day 1 up to a maximum of 6 months after the initial occurrence of the event.

7.6.5 On-Treatment Hepatitis C Management

If a subject tests positive for HCV RNA at screening or develops signs or symptoms of active hepatitis C, Sponsor recommends that local medical practice be followed at the discretion of the Investigator. Study medications may be continued without dose interruption. Should subject's primary treating physician or the Investigator decide to initiate hepatitis C treatment, drug-drug interaction should be evaluated. Subject should return to the clinic for scheduled or unscheduled follow up visit(s) according to local medical practice for laboratory evaluation.

7.6.6 On-Treatment Hepatitis D Management

If a subject tests positive for HDV at screening or develops signs or symptoms of active hepatitis D, Sponsor recommends that local medical practice be followed at the discretion of the Investigator.

8 QUALITY CONTROL AND QUALITY ASSURANCE

This study will be conducted in accordance with International Conference on Harmonisation Good Clinical Practice (ICH GCP) and the U.S. Code of Federal Regulations (CFR) applicable to clinical studies (45 CFR Part 46, 21 CFR Part 50, 21 CFR Part 56, 21 CFR Part 312, and/or 21 CFR Part 812).

The investigator agrees to be responsible for implementing and maintaining quality control and quality assurance systems to ensure that trials are conducted and data are generated, documented, and reported in compliance with the protocol, accepted standards of GCP, and all applicable federal, state, and local laws, rules and regulations relating to the conduct of the clinical study.

The investigator also agrees to conduct the study in an efficient and diligent manner and in conformance with this protocol; generally accepted standard of GCP; and all applicable federal, state, and local laws, rules and regulations relating to the conduct of the clinical study.

The investigator must allow study-related monitoring, audits, and inspection by the IRB, sponsor (or designee), government regulatory agencies, and, if applicable, University compliance and quality assurance groups of all trial-related documents and procedures.

The investigator shall prepare and maintain accurate study documentation in compliance with GCP standards and applicable federal, state, and local laws, rules and regulations.

The IHV Clinical Research Unit (CRU) will perform internal quality management of study conduct, data and biological specimen collection, documentation and completion. An individualized quality management plan will be developed.

Quality control (QC) procedures will be implemented beginning with the data entry system and data QC checks that will be run on the database will be generated. Any missing data or data anomalies will be addressed.

9 STATISTICAL CONSIDERATIONS

9.1 General Consideration & Populations for Analyses

The primary analysis for efficacy analyses will employ intention-to-treat (ITT) population defined as the full analysis population, which will include all subjects who have received at least 1 dose of the study drug.

The secondary analysis for efficacy analyses will employ a per-protocol (PP) population, which will include all subjects who have received at least one dose of the study drug, and have not committed any major protocol violation, including the violation of key eligibility criteria. In the Week 24 (or Week 48) per-protocol analysis, subjects meeting any of the following criteria will be excluded:

- a. Subjects who do not have on-treatment HIV-1 RNA and/or HBV DNA in the Week 24 (or Week 48) analysis window, except when missing data is due to discontinuation of study drug for lack of efficacy.
- b. Subjects who were removed from study due to nonadherence to study drug or due to protocol violation by the subject.

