3.2.9 Management of Virologic Rebound

Subjects who meet the criteria listed below will be considered to have virologic rebound:

HIV-1 Virologic Rebound:

- At any visit, a rebound in HIV-1 RNA ≥ 50 copies/mL, which is subsequently confirmed at the following scheduled or unscheduled visit; OR
- At any visit, a $>1 \log_{10}$ increase in HIV-1 RNA from nadir which is subsequently confirmed at the following scheduled or unscheduled visit.

Following unconfirmed virologic rebound, subjects will be asked to return to the clinic for a scheduled or unscheduled blood draw (2 to 3 weeks after the date of the original test that resulted in HIV-1 RNA virologic rebound) for confirmation of virologic rebound. If virologic rebound is confirmed at the scheduled or unscheduled visit and the HIV-1 RNA is ≥ 500 copies/mL, the blood sample from the confirmation test will be the primary sample used for HIV-1 genotypic and phenotypic testing. Subjects with documented non-adherence within 72 hours of the visit may not be tested for resistance. Resistance testing will be conducted on a case-by-case basis. Any subject may be discontinued at Investigator's discretion.

[figure not shown]
If no resistance is detected, the subject may remain on study drug and a repeat HIV-1 RNA should be repeated (approximately 2 to 3 weeks after date of test with HIV-1 RNA ≥ 50 copies/mL). Investigator should carefully evaluate the benefits and risk of remaining on the study drug for each individual subject and document this assessment in the medical record.

Subject who are noncompliant on an ongoing basis will be considered for discontinuation per the Investigator's discretion.

For subjects who are off study drug but remain on study, it will be the Investigator's discretion to manage virologic rebound.

Figure 6-1 illustrates the algorithm for the management of subjects who meet the criteria for HIV-1 virologic rebound.

Figure 6-1: Virologic Rebound Schema for HIV-1.

HBV Virologic Rebound:

- At any visit, after achieving HBV DNA <29 IU/mL, a rebound in HBV DNA ≥29 IU/mL, which is subsequently confirmed at the following scheduled or unscheduled visit; OR
- At any visit, a >1 log₁₀ increase in HBV DNA from nadir which is subsequently confirmed at the following scheduled or unscheduled visit.

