9.2 Sample Size Determination

This study is anticipated to screen up to 75 subjects to enroll approximately 60 subjects coinfected with HIV and HBV, who are currently on antiretroviral therapy. The primary analysis endpoint to evaluate treatment efficacy used to compute the sample size is the observed HIV-1 viral suppression rate. A true suppression rate at Week 24 of at least 91% would be considered active in this patient population. An exact binomial test with a 0.05 type I error rate will have 84% power to detect the difference between the null hypothesis proportion (number of suppressed/total number treated) of 0.773 (based on published results) and the research hypothesis proportion of 0.910 (our educated guess on the desired rate of success) when the sample size is 60.

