9.2.2.1 US FDA Snapshot Algorithm for HIV-1 Efficacy Analyses

The analysis window at Week 24 is defined as from Study Day 140 to Day 196. All HIV-1 RNA data collected on-treatment will be used in the snapshot algorithm. HIV-1 Virologic outcome will be defined as the following categories:

- **HIV-1 Virologic Success:** this includes subject who have the last available HIV-1 RNA < 50 copies/mL in the Week 24 analysis window while on study treatment.
- **HIV-1 Virologic Failure:** this includes subjects who
 - a. Have the last available HIV-1 RNA \geq 50 copies/mL in the Week 24 analysis window while on study treatment, or
 - b. Do not have on-treatment HIV-1 RNA data in the Week 24 analysis window and
 - 1) Discontinue study drug prior to or in the Week 24 analysis window due to lack of efficacy, or
 - 2) Discontinue study drug prior to or in the Week 24 analysis window due to reasons other than adverse events (AE), death, or lack of efficacy and have the last available HIV-1 RNA up to 1 day after the premature discontinuation of the study drug \geq 50 copies/mL.
- **No HIV-1 Virologic Data in the Week 24 analysis window:** this includes subjects who do not have on-treatment HIV-1 RNA data in the Week 24 analysis window because of the following:
 - a. Discontinuation of the study drug prior to or in the Week 24 analysis window due to AE or death (regardless of whether the last available HIV-1 RNA up to 1 day after the premature discontinuation of the study drug < 50 copies/mL or not), or
 - b. Discontinuation of the study drug prior to or in the Week 24 analysis window due to reasons other than AE, death, or lack of efficacy (e.g., withdrew consent and loss to follow-up) and the last available HIV-1 RNA up to 1 day after the premature discontinuation of the study drug is < 50 copies/mL, or
 - c. Missing data during the window but remains on study drug.

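### The per-protocol set drops some HIV-1 virologic failures that the plan itself defines, because its exception follows the recorded stop reason and not the viral load

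*Combined protocol and SAP*

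**What the plan says.** Section 9.1 sets out two efficacy populations. For the first, "The primary analysis for efficacy analyses will employ intention-to-treat (ITT) population defined as the full analysis population", meaning everyone who took at least one dose. The second is a per-protocol set for secondary efficacy analysis. It excludes major protocol violators and, for each time point, two further groups. Criterion (a) excludes subjects without on-treatment HIV-1 RNA and/or HBV DNA in the analysis window, "except when missing data is due to discontinuation of study drug for lack of efficacy". Criterion (b) excludes subjects removed from study for nonadherence or protocol violation.

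Section 9.2.2.1 defines the Week 24 window as Day 140 to Day 196. It names two kinds of HIV-1 virologic failure among subjects with no on-treatment value in that window:

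- b.1: the subject stopped for lack of efficacy.
- b.2: the subject stopped "due to reasons other than adverse events (AE), death, or lack of efficacy", and the last HIV-1 RNA, up to one day after stopping, was at least 50 copies/mL.

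Section 3.2.8 also counts HIV-1 RNA of at least 50 copies/mL, or HBV DNA of at least 29 IU/mL, at study drug discontinuation as virologic failure, whatever the reason for stopping. For HBV, section 9.2.2.2 treats every subject without window data as a failure.

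**The concern.** The exception in 9.1(a) shows that the plan does not want the per-protocol set to lose treatment failures merely because they left before the window. But the exception depends on the recorded reason for stopping, and the failure definitions depend on the viral load. Section 3.2.5 lists lack of efficacy, subject request and noncompliance as separate grounds for stopping and gives no rule for choosing when more than one applies. Section 4 says that enrolled subjects may or may not be suppressed at entry, so someone who is viraemic when they withdraw or are lost to follow-up is a realistic case. Such a subject is a documented failure in one analysis and missing from the other, and what decides this is an entry on a form in an open-label study.

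At stake is how far the per-protocol rate can support the primary result. There is no control arm in which the same exclusion would also operate, so any upward shift goes straight into the reported percentage.

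**Working it through.** **1. The plan's own figure.** Section 9.2 gives n = 60, a null of 0.773, an alternative of 0.910, an exact binomial test at 0.05 and 84% power. The number of sides is not stated.

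- P(X ≥ 52 | 60, 0.773) = 0.0514, which exceeds 0.05.
- P(X ≥ 53 | 60, 0.773) = 0.0237. The cut-off is therefore 53/60 = 88.3%, both for a one-sided 0.05 and for an upper tail of 0.025.
- Power = P(X ≥ 53 | 60, 0.910) = 83.1%, within one point of the stated 84%.

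The null is expressed over all subjects treated, so this calculation belongs to the full analysis population. Nothing below changes it.

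**2. HIV-1 RNA missing from the window: the two sections side by side.**

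| Why there is no on-treatment value | Section 9.2.2.1 | Section 9.1(a) |
|---|---|---|
| Stopped, lack of efficacy | Failure (b.1) | Kept |
| Stopped, other reason, last value ≥50 | Failure (b.2) | Excluded |
| Stopped, other reason, last value <50 | No data | Excluded |
| Stopped, adverse event or death | No data | Excluded |
| Still on drug, value missing | No data | Excluded |

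Only the second row is inconsistent. A subject who stops but has an on-treatment value inside the window is untouched by (a).

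**3. Size.** Let S be the number of successes, N the number in the set if b.2 failures are kept, and f the number of b.2 failures.

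- Rate with them kept: S/N.
- Rate under 9.1(a): S/(N − f).
- Difference: S·f / [N(N − f)], which is zero when f = 0 and positive otherwise.

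The documents give no value for S or f, so both are assumed here, with N = 60 and no other exclusions.

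| f | S = 52: kept → dropped | Shift | S = 54: kept → dropped | Shift |
|---|---|---|---|---|
| 0 | 86.7% → 86.7% | 0 | 90.0% → 90.0% | 0 |
| 1 | 86.7% → 52/59 = 88.1% | 1.5 points | 90.0% → 54/59 = 91.5% | 1.5 points |
| 2 | 86.7% → 52/58 = 89.7% | 3.0 points | 90.0% → 54/58 = 93.1% | 3.1 points |
| 3 | 86.7% → 52/57 = 91.2% | 4.6 points | 90.0% → 54/57 = 94.7% | 4.7 points |

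Each such subject is worth about 1.5 points.

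**4. The *and/or*.** Take a subject with HIV-1 RNA in the window and no HBV DNA. If (a) means that either value missing is enough, the subject leaves both per-protocol analyses. If it means the value for the endpoint concerned, the subject leaves only the HBV analysis. If it means both values missing, the subject stays in both. The text supports all three readings. Under the first, the HIV-1 analysis can lose a documented success as easily as a documented failure, and the same happens to the HBV analysis when HIV-1 RNA is the missing value.

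**The case against.** The best defence is that little depends on this. The per-protocol analysis is secondary. In the primary analysis every b.2 subject stays in the denominator as a failure, and missing HBV DNA counts as failure. A per-protocol set is also meant to describe subjects who followed the protocol: criterion (b) openly excludes those removed for nonadherence, and some b.2 subjects will be exactly those. Returning them would change what the per-protocol rate estimates. The affected group is narrow and may be empty.

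Most of this stands. It limits the importance of the point, and it is a good reason to leave criterion (b) alone. It does not explain criterion (a), which on its own removes viraemic subjects who withdrew or were lost and who were never judged nonadherent.

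A reader might go further in three ways that the documents do not support.

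- *The trial's test is compromised.* With 52 successes, the exact upper tail against 0.773 is 0.0514 in 60 subjects and 0.027 in 59, so one dropped failure could cross 0.05. But the plan nowhere applies that test to the per-protocol set. Nor is 0.910 a pass mark for an observed rate; it is the true rate assumed for power.
- *The protocol pushes viraemic subjects out as noncompliant.* Section 3.2.9 says "Subject who are noncompliant on an ongoing basis will be considered for discontinuation", at the investigator's discretion. It also allows a subject with rebound and no detected resistance to remain on study drug with repeat testing.
- *All the per-protocol exclusions favour the drug.* The *and/or*, criterion (b) and the major-violation rule can each remove successes. The direction is fixed only for the b.2 subjects.

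**Conclusion.** The inconsistency is real and limited. Criterion 9.1(a) agrees with failure rule b.1 and disagrees with b.2 and section 3.2.8, so some failures by the plan's own definition leave the secondary per-protocol denominator for HIV-1. For that subset the effect is upward or nil, at about 1.5 percentage points per subject in a set of 60. The size rests entirely on assumed counts. The net direction of all the per-protocol rules together cannot be determined from the text. The *and/or* is a separate ambiguity of uncertain direction: two analysts could build different sets from the same data. The point is worth correcting because it is cheap to correct and the per-protocol rate will be read beside the primary one. It gives no reason to doubt the primary analysis or the sample size.

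**What to change.** Amend 9.1(a) in two respects, before the per-protocol set is drawn up.

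1. Make it endpoint-specific: missing HIV-1 RNA excludes a subject from the HIV-1 per-protocol analysis only, and missing HBV DNA from the HBV analysis only.
2. Widen the exception. For HIV-1, add subjects classed as virologic failure under 9.2.2.1 b.2. For HBV, add subjects whose HBV DNA was at least 29 IU/mL at study drug discontinuation, as in 3.2.8. The two are worded differently because the HIV-1 algorithm has a no-data category for stops due to adverse event or death, and the HBV method has none.

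Leave criterion (b) as it stands, and report beside the per-protocol result how many virologic failures it excluded, so that a reader can see what they would have done to the rate.

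The cost is a few lines of text and no new data. The per-protocol rate will be slightly lower if any such subjects occur.
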